### Sample size

This trial was a difference test design, the primary outcome measure was the change of the ratio of LH/FSH from baseline at the end of treatment. Based on the results of our pilot study and previous studies, we anticipated a mean difference in the ratio of LH/FSH was 1.2 (SD, 0.8) in CPA/EE group, and 1.68 (SD, 0.2) in Tung's acupuncture group. Sample size was determined with a 0.05-probability of a type I error and 80% power, 2 sided test with a 20% attrition rate. 30 patients will be needed for each group, which implied a total sample size of 60 participants for the entire trial.

### Statistical analysis

Statistical analysis performed using SPSS 13.0 statistics software (SPSS Inc, Chicago, IL, USA) and the statistician was blinded from group allocation. The Kolmogorov-Smirnov test was used to test the normal distribution of continuous variables. Continuous variables were presented by mean (standard deviation) if they were normally distributed or by median with interquartile range if they are not normally distributed. The modified intention-to-treat (ITT) approach was used to analyze the study group, all subjects with at least having one treatment data in randomized groups were included. A paired samples t test or Wilcoxon Matched-Pairs SignedRanks test was examined to compare the differences between the quantitative indices before and after treatment in one group, while an independent sample t test or Mann-Whiney U test was used for comparison between groups. The entire statistical test used bilateral examination and estimation of the median with 95% CI was calculated.

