## Outcome measurements

The change in LH/FSH ratio from baseline at end of treatment was considered as the primary outcome in this study, and secondary outcomes include the changes in BMI, FSH, LH, TT, ovarian volume, polycystic ovary number and menstrual frequency at week 12 and 24 from baseline. The blood samples were measured at the 2-3rd Day of menstrual cycle during the baseline period, after the last treatment and 12-week follow-up period. If no ovulation or bleeding had occurred during the period, the measurements were taken one week after the end of treatment and 12-week follow-up period. The sex hormones were analyzed by chemiluminescent microparticle immunoassay at the medical laboratory of Beijing Hospital of Integrated Traditional Chinese and Western Medicine.

The polycystic ovary number and volume were measured by ultrasound, which were together with BMI and menstrual frequency taken 3-7th days after menstruation during the baseline period, after the last treatment and 12-week follow-up period. The polycystic ovary number was defined as the number of ovaries with cysts/follicles (>12 cysts), the ovarian volume was measured in three dimensions by an experienced sonographer who was blinded to the group.

Safety evaluation included acupuncture related adversary events such as hematoma, fainting, severe pain, post-treatment soreness and local infection during and after acupuncture, as well as

CPA/EE related adversary events like vomiting, nausea, headache and skin reactions during taking pills.

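### The primary comparison of change in LH/FSH is left as a t test or a Mann-Whitney test without a written choice rule, an unequal-variance form, an interval for the mean difference, or use of the collected baseline

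*Combined protocol and SAP*

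**What the plan says.** The Outcome measurements section fixes the primary outcome: "The change in LH/FSH ratio from baseline at end of treatment was considered as the primary outcome in this study". It also shows that a baseline hormone value exists for that outcome: "The blood samples were measured at the 2-3rd Day of menstrual cycle during the baseline period".

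The Sample size section plans on unequal spread: "we anticipated a mean difference in the ratio of LH/FSH was 1.2 (SD, 0.8) in CPA/EE group, and 1.68 (SD, 0.2"). It adds: "Sample size was determined with a 0.05-probability of a type I error and 80% power, 2 sided test with a 20% attrition rate". The result is 30 per group.

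The Statistical analysis section contains four relevant statements.

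- Normality: "The Kolmogorov-Smirnov test was used to test the normal distribution of continuous variables".
- Presentation: "Continuous variables were presented by mean (standard deviation) if they were normally distributed or by median with interquartile range" if not.
- Between-group test: "an independent sample t test or Mann-Whiney U test was used for comparison between groups".
- Interval: "estimation of the median with 95% CI was calculated".

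The check is tied in writing only to how data are presented. That it also selects the test is the natural reading, but it is not stated. No significance level is given for the check. Nothing says whether it is run per arm or on both arms together, or on raw values or changes. The form of the t test is not given, no interval for a between-group difference is named, and no covariate is mentioned.

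**The concern.** A primary analysis should be fixed before the data are seen, and it should estimate the quantity on which the trial was sized. Here the choice between a comparison of means and a rank comparison appears to follow from the outcome data, through a rule that two analysts could apply differently.

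The planned SDs make the choice matter. The variance ratio is (0.8/0.2)² = 16. At that ratio a pooled t test is sensitive to uneven completer numbers, and a Mann-Whitney test responds to the difference in spread as well as to a difference in location. At stake are the significance verdict on the primary outcome, a modest drift in type I error, and whether the report contains an interval for the mean difference. The baseline is a separate matter: it is already collected, and adjustment would remove the effect of chance baseline imbalance.

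**Working it through.** **Inputs.** From Sample size: means 1.2 and 1.68, SDs 0.8 (CPA/EE) and 0.2 (acupuncture), two-sided 5%, 80% power, 20% attrition. From Randomization and blinding: 1:1 allocation. Assumed, because the documents do not give them: normal data, the completer splits below, and the pre/post correlations.

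**1. The plan's own figure.** Difference = 1.68 − 1.2 = 0.48.

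n per arm = (0.8² + 0.2²)(1.960 + 0.842)² / 0.48² = 0.68 × 7.849 / 0.2304 = 23.2, so 24. Then 24/0.8 = 30, an exact match. At 24 per arm, power is 81.4% by the normal approximation and 79.7% by the pooled t distribution (46 df). By Welch (25.9 df) it is 78.4%.

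**2. The two listed tests** (40,000 simulated trials per setting; sizes are CPA/EE v acupuncture).

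| Completers | Error, pooled t | Error, Welch | Error, Mann-Whitney |
|---|---|---|---|
| 24 v 24 | 5.2% | 4.8% | 7.2% |
| 22 v 26 | 7.4% | 5.0% | 8.8% |
| 26 v 22 | 3.8% | 5.0% | 6.4% |
| 20 v 28 | 9.8% | 5.0% | 10.0% |
| 28 v 20 | 2.7% | 5.1% | 5.3% |

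Power at 24 v 24 is 79.6% (pooled), 78.4% (Welch) and 75.0% (Mann-Whitney). At the planned difference, pooled t and Mann-Whitney disagree on significance in about 12% of trials.

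**3. Why uneven arms matter for a pooled test.** At 22 v 26 the expected pooled variance is (21 × 0.64 + 25 × 0.04)/46 = 0.314. The pooled SE is √[0.314 × (1/22 + 1/26)] = 0.162. The true SE is √(0.64/22 + 0.04/26) = 0.175, so the pooled SE is about 7% too small. At 26 v 22 the values are 0.175 and 0.163, about 8% too large. At 24 v 24 the two formulas coincide.

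**4. How often arms are uneven.** With completers Binomial(30, 0.8) in each arm, a gap of 4 or more occurs in 25.6% of trials and of 8 or more in 1.5%. Averaged over this, error is 5.6% for pooled t and 5.1% for Welch.

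**5. The Kolmogorov-Smirnov rule**, read as pooled t unless the check rejects at 5%, at 24 v 24.

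| Reading | Error | Power at 0.48 | Mann-Whitney chosen, null / difference |
|---|---|---|---|
| Per arm, standard critical values | 5.2% | 79.6% | 0 / 0% |
| Combined, standard | 5.0% | 76.6% | 6 / 22% |
| Per arm, estimated-parameter values | 5.9% | 79.3% | 10 / 10% |
| Combined, estimated-parameter | 6.2% | 74.3% | 74 / 90% |

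**6. Baseline adjustment.** Assume equal pre and post SD s in both arms, with 2s²(1 − ρ) equal to 0.64 and 0.04 by arm. An average ρ of 0.7 then means s² = 0.34/(2 × 0.3) = 0.567, with arm correlations 1 − 0.64/1.133 = 0.44 and 1 − 0.04/1.133 = 0.96. The other rows follow in the same way (20,000 trials, 24 v 24).

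| Average ρ | HC3 ANCOVA power | Against pooled t on change (79.6%) |
|---|---|---|
| 0.7 | 83.1% | +3.5 |
| 0.8 | 80.8% | +1.2 |
| 0.9 | 78.5% | −1.1 |
| 0.95 | 77.3% | −2.3 |

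HC3 error at 24 v 24 is 4.6% to 4.9%. A one-SE chance baseline imbalance shifts the unadjusted change comparison by 0.065, 0.054, 0.038 and 0.026 in the four rows (14%, 11%, 8% and 5% of 0.48). ANCOVA removes that shift.

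**The case against.** The case for leaving the plan alone is substantial, and much of it stands.

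- *The normality check is specified.* True: Kolmogorov-Smirnov is named. Only its level, its unit and its link to the choice of test are missing.
- *A t test on change is valid.* It is. A reader might infer from the 16-fold variance ratio that the trial's error rate is badly inflated. The documents do not support that: they do not say that the t test is pooled, equal arms give about 5%, and under the planned attrition the average is 5.6% even if it is pooled. Error near 10% needs 20 v 28 completers, and gaps that large in either direction arise in 1.5% of trials.
- *The rank test's 7% is the plan's error.* A reader might infer this too. It applies only if Mann-Whitney is always run and read as a location test. It bounds that branch and not the whole rule.
- *Five points of power are lost.* The fall from 79.6% to 74.3% needs the check to be run on both arms together with estimated-parameter critical values. Per-arm readings lose almost nothing, and the text indicates neither reading.
- *The covariate is a preference.* Omitting it is not an error. Nor is a large gain available on plausible inputs: power of 87% to 94% appears if one correlation (0.7 down to 0.3) is applied to both arms, but change SDs of 0.8 and 0.2 would then require baseline SDs differing fourfold between randomised arms.
- *Every rate assumes normal data, while the rank branch exists for other data.* This stands. With shifted lognormal changes at the same SDs and 24 v 24, Welch error as a test of means is about 6.5% (log-SD 0.5) and 8.6% (log-SD 0.8). Mann-Whitney reaches about 21% and 40% on the same criterion, so switching to ranks does not repair a comparison of means.

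**Conclusion.** The concern holds as an incomplete and improvable specification, not as a flaw that invalidates the trial or its sample size. What is established from the text is that there is no written rule for choosing the primary test, no stated variance form despite planned SDs of 0.8 and 0.2, no interval for the mean difference of 0.48 behind the sample size, and no use of the baseline.

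The main practical consequence is that about one trial in eight would change its significance verdict according to which listed test is run. The type I error consequence is smaller and conditional on a pooled test with uneven completers. These sizes rest on normality and on the planned SDs. The sign of the power change from adjustment rests on an unknown correlation. Attending to this is worthwhile because the remedy is cheap, and confidence in the reading of the text is high.

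**What to change.** Pre-specify one primary analysis: ANCOVA of end-of-treatment LH/FSH on group and baseline LH/FSH with HC3 standard errors, reporting the adjusted mean difference with its 95% CI. The group coefficient is identical whether the end value or the change is modelled, so the stated primary outcome is unchanged. Report Welch's t on change, and Mann-Whitney with a median-based interval, as sensitivity analyses and not as branches chosen by a normality test. Adjusting the continuous secondary outcomes for their own baselines is optional.

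The cost is SAP wording and a few lines of code, with no new data.

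- **Software.** The plan names SPSS 13.0. The documents do not show whether it offers HC3, so the analysis should be run in a package that does.
- **Power.** It may be about 1 to 2 points below pooled t if the average pre/post correlation is 0.9 to 0.95. The Welch sensitivity analysis has about 1 point less (78.4% v 79.6%). Reaching 80% by Welch needs 25 evaluable per arm, or 25/0.8 = 31.25, so 32 randomised. The pooled t test also falls just short at 24, so this shortfall is not created by the change.
- **Skewness.** Neither Welch nor HC3 is guaranteed to hold 5% with strongly skewed changes, and the report should say so.
- **Timing.** Most of the document is in the past tense. If the data have already been analysed, the adjusted result must be labelled a sensitivity analysis.
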